### **9.3.2. Safety Analyses**

Adverse events (AEs) occurring during the study will be recorded and classified according to MedDRA terminology. Those occurred one or after treatment are considered as treatment-emergent. All reported TEAEs will be summarized, in terms of the number of subjects reporting events, system organ class, preferred term, severity, relationship to study drug, and seriousness. For summarization of event causality and seriousness, subjects will be counted only once within a system organ class or preferred term using the event with the event with the greatest relationship for causality and the event with the highest severity. A summary of TEAEs leading to discontinuation will also be provided.

A by-subject listing of any SAEs will be provided and all SAEs will be summarized by severity and relationship to study treatment.

Clinical laboratory test results will be summarized by visit and if applicable a shift table will be used to evaluate the shift in status from baseline at each visit.

## **9.4. Interim Analyses**

Due to the nature of the study design, data will be evaluated after each dosing cohort achieves a pre-specified milestone (e.g., 5 weeks after last subject's enrollment) before a decision is made to move forward with the next dosing cohort. In addition, a formal interim analysis of the data will be performed when all subjects finish 8 weeks after receiving the FHL treatment or have withdrawn from the study earlier.

### **9.4.1. Data Review Committee**

Due to the dose-escalation nature of the study design, safety data and subject photographs/videos will be evaluated by the DRC at Week 5 following GL treatment (3 weeks after FHL treatment) for each cohort before a decision is made to move forward with the next and subsequent doses. If the DRC elects not to proceed with the FHL injection in a given dose cohort, subjects will be followed for 14 weeks from the time of treatment (Day 1).

Dose escalation for FHL may be stopped at the discretion of the DRC as outlined in the DRC Charter.

The full details for the roles and responsibilities of the DRC will be detailed in the study-specific DRC charter.

## 10. RECORDS MANAGEMENT

### 10.1. Data Collection

For this study, all protocol-specified data will be recorded in the source documents, and data will be entered on the eCRFs from the source documents. In addition to signature confirmation that a subject meets the study eligibility criteria, upon each subject's completion of the study, the investigator will sign a statement indicating that all pages of the subject's case report have been reviewed. Signature stamps and "per signatures" are not acceptable.

It is Revance's policy that the study data be verifiable with the source data that necessitates access to all original recordings, laboratory reports, and other records for each subject. The investigator must, therefore, agree to allow access to subjects' records, and source data must be made available for all study data. Subjects (or their legal representatives) must also allow access to their medical records. Subjects will be informed of the importance of increased record access and permission granted by signature on the informed consent document prior to any screening procedures.

Checks will be performed to ensure the quality, consistency, and completeness of the data. Instances of missing or un-interpretable data will be resolved with the investigator or Study Coordinator. Data queries will be sent to the study center. Site personnel will be responsible for providing resolutions to the data queries and for correcting the eCRFs, as appropriate. All unused Revance or designee study materials and binders must be returned to Revance or designee upon completion of the study.

The investigator must keep written or electronic source documents for every subject participating in the clinical study. The subject file that identifies the study in which the subject is participating must include the subject's available demographic and medical information including:

- Name
- Contact information
- Date of birth
- Sex
- Medical history
- Concomitant diseases
- Concomitant therapies/medication
- Study visit dates
- Performed examinations, evaluations, and clinical findings
- Investigational product administration
- AEs, SAEs, or pregnancy (as applicable)

Additionally, any other documents with source data, especially original printouts of data that were generated by technical equipment must be included in the subject's source document (e.g., laboratory value listings). All these documents must have at least the subject's initials, study number, and the date of the evaluation.

The data recorded during the study will be documented in the eCRF and/or the study-specific forms. Before or at study termination, all data must be forwarded to Revance or designee. The data will be recorded, evaluated, and stored in anonymous form in accordance with data-protection regulations.

Subjects will authorize the use of their protected health information (PHI) during the informed consent process in accordance with the applicable privacy requirements. Subjects who deny permission to use and disclose PHI will not be eligible to participate in the study. The investigator will ensure that the study documents forwarded to Revance or their designee, and any other documents, contain no subject names or other PHI, such as medical record number or date of birth.

Any amendments and corrections necessary will be undertaken in both the source documents and eCRFs (as appropriate) and countersigned by the investigator, or documented designee, stating the date of the amendment/correction. Errors must remain legible and may not be deleted with correction aids. The investigator must state his/her reason for the correction of any data. In the case of missing data/remarks, the entry spaces provided in the eCRF should be cancelled out to avoid unnecessary follow-up inquiries.

Regulatory authorities, the IRB/IEC and/or Revance's Quality Assurance department (or designee) may request access to all source documents, eCRFs, and other study documentation for on-site audit or inspection. The investigator must guarantee direct access to these documents. The eCRFs will be kept by Revance or designee in a secured area. Clinical data will be recorded in a computer format for subsequent statistical analyses. Data files will be stored on electronic media with a final master data file kept by Revance or designee after descriptive and statistical analyses and reports have been generated and are complete.

## **10.2. File Management at the Study Center**

It is the responsibility of the investigator to ensure that the study center maintains all source and essential documents in accordance with ICH Guidance for Industry E6 (R2) Good Clinical Practice: Consolidated Guidance, Section 8 – Essential Documents for the Conduct of a Clinical Study.

## **10.3. Records Retention at the Study Center**

It is a Revance requirement that all investigators participating in clinical studies maintain detailed clinical data for one of the following periods:

- Country-specific requirements, or
- A period of at least 2 years following the last approval of a marketing application approved by a Regulatory Authority in an ICH region or until there are no pending or contemplated marketing applications in an ICH region, or,
- A period of 2 years after Revance notifies the investigator that the data will not be submitted for review by any Regulatory Authority

Regardless of applicable retention period, the investigator must not dispose of any records or essential documents relevant to this study without either (1) written permission from Revance, or (2) providing an opportunity for Revance to collect such records. The investigator shall take

responsibility for maintaining adequate and accurate electronic or hard copy source documents of all observations and data generated during this study. Such documentation is subject to inspection by Revance or designee and relevant regulatory agencies. If the investigator withdraws from the study (e.g., relocation, retirement) all study-related records should be transferred to a mutually agreed upon designee. Notice of such transfer will be provided to Revance in writing.

Topic	Percentage
The concept of a 'smart city'	~75%
Smart cities in the news media	~95%
Smart cities in the government	~90%
Smart cities in the private sector	~85%
Smart cities in the academic world	~80%
Smart cities in the public sector	~70%
Smart cities in the international arena	~90%

## **12. ETHICS AND RESPONSIBILITY**

This study must be conducted in compliance with the protocol, the ICH Guidance for Industry E6 (R2) Good Clinical Practice: Consolidated Guidance and the applicable regulatory requirements. Investigators must submit all essential regulatory documentation, as required by local and national regulations (including IRB/IEC approval of the protocol and informed consent form) to Revance or designee before investigational product will be shipped to the study center.

A horizontal bar chart consisting of 15 black bars of varying lengths. The bars are arranged in two groups: a top group of 8 bars and a bottom group of 7 bars. The bars in the top group are generally longer than those in the bottom group. The first bar in the top group is the longest, followed by the second, and so on. The last bar in the top group is shorter than the first bar in the bottom group. The bars in the bottom group are also arranged in a descending order of length from left to right.

A bar chart illustrating the distribution of 1000 samples across 10 categories. The x-axis represents the category index (0 to 9), and the y-axis represents the frequency of samples (0 to 100). The distribution is highly right-skewed, with the highest frequency in category 0 (approximately 950) and the lowest in category 9 (approximately 50).

Category	Frequency
0	~950
1	~10
2	~10
3	~10
4	~10
5	~10
6	~10
7	~10
8	~10
9	~50

**LIST OF ABBREVIATIONS AND DEFINITIONS OF TERMS**

Abbreviation	Term
AE	Adverse Event
CI	Confidence interval
DAXI	DaxibotulinumtoxinA
FASE	Facial Age Self Evaluation
DRC	Data Review Committee
FASE	Facial Age Self Evaluation
FHL	Forehead lines
GAIS	Global Aesthetic Improvement Scale
GL	Glabellar lines
IGA-FWS	Investigator Global Assessment Frown Wrinkle Severity
IGA-FHWS	Investigator Global Assessment Forehead Wrinkle Severity
IM	Intramuscular
MedDRA	Medical Dictionary for Drug Regulatory Affairs
PFWS	Patient Frown Wrinkle Severity
PFHWS	Patient Forehead Wrinkle Severity
PI	Principal Investigator
SAE	Serious adverse event
SAP	Statistical analysis plan
TEAE	Treatment-emergent adverse event
UPT	Urine pregnancy test
WOCBP	Women of childbearing potential

## 1. INTRODUCTION

The efficacy and safety of botulinum toxin type A for the treatment of FHL has been evaluated in a number of studies. Solish et al. (2016) conducted the first large-scale, multicenter study of onabotulinumtoxinA with 40 U or 30 U total injected into both the frontalis and the glabellar complex. Complementary treatment of the glabellar complex in conjunction with the frontalis provides more satisfactory results and reduces the potential for eyebrow ptosis. At 4 weeks after the first injection, 94.4% of subjects at the 40 U dose and 84.2% of subjects at the 30 U dose were satisfied or very satisfied with the reduction in FHL severity. A longer duration of effect was noted in the 40 U dose group. There was no observed dose response noted in the incidence of eyebrow- or eyelid-related AEs in either the 40 U and 30 U dose groups. The overall incidence of eyebrow ptosis across both doses (coded as facial paresis) was low at 2.3%.

The Sponsor, Revance Therapeutics, Inc. (Revance), has conducted 5 studies to examine the safety and

This statistical analysis plan (SAP) describes the objectives of the study and the safety and efficacy assessments that are collected. The safety endpoints and the efficacy endpoints are defined, and the statistical methods used to analyze them are presented. Table shells for the planned end-of-text tables, figures, and listings are included in a separate document, but the titles are specified following the text of the SAP.

## 2. STUDY OBJECTIVES

### 2.1 Objectives

[figure not shown]
#### 2.1.1 Primary Objective

[figure not shown]
The primary study objective is to evaluate the efficacy and safety of DaxibotulinumtoxinA (DAXI) for Injection in the treatment of dynamic Forehead Lines (Frontalis) (FHL).

## **2.2 Trial Endpoints**

### **2.2.1 Efficacy Endpoints**

The primary efficacy endpoint is the proportion of subjects achieving a score of 0 or 1 (none or mild) in FHL severity at maximum eyebrow elevation at 4 weeks after FHL treatment (Week 6) on the Investigator Global Assessment Forehead Wrinkle Severity (IGA-FHWS) scale.

## **2.2.2 Safety Endpoints**

The primary safety endpoint is the incidence, severity, and relationship to study drug of TEAEs and SAEs during the overall study duration.

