### **8.5.2. Assessment and Reporting Requirements**

The investigator will assess subjects after GL and FHL treatment and at each subsequent study visit for the occurrence of AEs. To avoid bias in eliciting AEs, subjects should be asked the following non-leading question: "How have you felt since your last visit?" All AEs (serious and non-serious) will be collected from signing of the ICF until the Final Evaluation Visit at each visit. Any AE reported by the subject must be recorded on the source documents and eCRFs.

All AEs will be collected from Day 1 until Week 38 or Final Evaluation Visit at the time points specified in the SOA (Section 1.3).

Medical occurrences that begin before the start of study intervention but after obtaining informed consent will be recorded on the Medical History/Current Medical Conditions section of the eCRF not the AE section.

All SAEs will be recorded and reported to Revance or designee immediately within 24 hours of their awareness of the event. All fatal or life-threatening SAEs should be telephoned to Revance or the designee's authorized representative as soon as the investigator learns of the event.

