### 3. OVERALL STUDY DESIGN AND PLAN

#### 3.1 Study Design

[figure not shown]
This is a phase 2a, multicenter, open-label, dose-escalation study to evaluate the safety and efficacy of DAXI for injection for the treatment of subjects with moderate to severe FHL in conjunction with GL treatment. This study will be conducted at 4 sites in the United States and Canada.

Subjects will be screened for eligibility and enrolled into the study after providing informed consent.

[figure not shown]
Approximately 60 subjects (18-65 years of age) with moderate to severe FHL will be enrolled

[figure not shown]
The total study duration will be up to 40 weeks including up to 2 weeks for screening. Subjects will be followed for a minimum of 24 weeks from GL treatment for safety or until all scores on the IGA-FWS and PFWS, as well as the IGA-FHWS and PFHWS return to baseline (Day 1 Visit prior to GL treatment) or until Week 38, whichever occurs first. Subjects will then have a Final Evaluation Visit. The intention is for subjects to be followed for a minimum of 24 weeks from FHL treatment (Week 26).

A Data Review Committee (DRC) will be used to review data from each cohort and will determine whether to proceed to the next cohort. If the DRC elects not to proceed with the FHL injection in a given dose cohort, subjects assigned to that cohort who have already received GL treatment will be followed for 14 weeks from the time of treatment (Day 1).

[figure not shown]

Statistical Analysis Plan for 1820202

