### 6.6 Safety Analyses

Safety summaries and analyses will be performed on the Safety and Safety FHL populations and will be presented by cohort and in total across cohorts. Descriptive statistics will be presented to summarize the safety data. By visit safety summaries will use denominators based on the number of subjects with valid observations at that visit unless otherwise specified.

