### 6.6.3 Adverse Events

All AEs will be recorded and classified on the basis of MedDRA terminology. All treatment-emergent AEs will be summarized by summary cohort and overall, system organ class, preferred term, severity, and seriousness. When summarizing events by causality and severity by subject, each subject will be counted only once within a system organ class or a preferred term by using the event with the greatest relationship and highest severity within each classification. Additionally, some summaries will present the number of AEs as well as incidence.

An overall summary of treatment-emergent AEs (TEAEs) will be provided. The number and percentage of subjects experiencing an AE, an SAE, a related AE, a related SAE, an AE of special interest, an AE leading to study discontinuation, and an AE resulting in death will be summarized.

All information pertaining to AEs noted during the trial will be listed by subject, detailing the verbatim description given by the Investigator, preferred term, system organ class, start date, stop date, severity, action taken regarding trial drug, corrective treatment, outcome, and drug relatedness. The event onset relative (in number of days) to the date of treatment for GL and FHL, as well as to the date of last treatment administration prior to the event, will be provided. In addition, a list of adverse events that lead to the subject's premature discontinuation of the trial will be provided. Serious adverse events (SAEs) will be listed by subject.

Statistical Analysis Plan for 1820202

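### Whole-study TEAE percentages compare dose cohorts over follow-up that runs from about Week 26 to Week 38 according to each subject's own response, with no common window

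*SAP*

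**What the plan says.** SAP 2.2.2 defines the endpoint with no cut-off week: "The primary safety endpoint is the incidence, severity, and relationship to study drug of TEAEs and SAEs during the overall study duration". SAP 6.6.3 reports it as a simple proportion: "The number and percentage of subjects experiencing an AE, an SAE, a related AE, a related SAE, an AE of special interest", with discontinuations and deaths added. SAP 6.6 says that safety summaries, for both the Safety and the Safety-FHL populations, "will be presented by cohort and in total across cohorts".

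Protocol 8.5.2 sets the collection period: "All AEs will be collected from Day 1 until Week 38 or Final Evaluation Visit". SAP 3.1 sets the end of follow-up: "Subjects will be followed for a minimum of 24 weeks from GL treatment for safety or until all scores on the IGA-FWS and PFWS", together with the two forehead scores, "return to baseline (Day 1 Visit prior to GL treatment) or until Week 38, whichever occurs first". SAP 3.1 then adds an intended minimum of 24 weeks counted from FHL treatment, which it gives as Week 26. The on-site visits around that time are at Weeks 22, 26, 30, 34 and 38 (Protocol 4.4).

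A separate rule covers cohorts in which the DRC withholds FHL treatment. Subjects there who have already had GL treatment are followed for 14 weeks from Day 1 (SAP 3.1). They belong to the Safety population (SAP 4.4) but not to Safety-FHL (SAP 4.5).

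The visible text has two features that help. SAP 6.1 summarises length of participation, without saying that this is by cohort. SAP 6.6.3 lists the onset day of each event relative to each treatment. SAP 6.6.1, on exposure, covers injected dose and not time.

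**The concern.** The percentage uses subjects as its denominator, so a subject who leaves at Week 26 counts as event-free for the weeks in which nobody asked. That is harmless if all cohorts are followed alike. Here the time of leaving depends on how long the treatment works, so observation time is itself an outcome of treatment. The documents make a link with dose plausible. Protocol 6 describes muscle weakening that depends on dose, and Protocol 2 cites a study of another toxin in which the higher-dose group had the longer effect.

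Safety is half of the primary objective, and the cohorts differ by FHL dose. A longer-acting dose could look less well tolerated only because it was watched for longer, or a true gradient could be blurred. Counting each subject once at the greatest severity and relationship carries the same dependence on observation time into those tables.

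**Working it through.** **The plan's own figures.** 38 weeks + 2 weeks of screening = 40 weeks. FHL treatment at Week 2 + 24 weeks = Week 26. 4 cohorts × 15 = 60 subjects. All three reproduce. The documents give no adverse event rate, so the rates below are assumptions.

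**Range of follow-up.** No visit is scheduled at Week 24. With a 24-week minimum from GL, the first scheduled exit is Week 26, which is also the SAP's stated intention. The longest-to-shortest ratio is 38/26 = 1.46 from Day 1, or 36/24 = 1.50 from FHL treatment.

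**Step 1: extreme contrast, same hazard everywhere.** Let p be the incidence by Week 26. With a constant hazard h = −ln(1 − p)/26, the incidence by Week 38 is 1 − exp(−38h) = 1 − (1 − p)^(38/26).

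| Assumed by Week 26 | By Week 38 |
|---|---|
| 10% | 14.3% |
| 20% | 27.8% |
| 30% | 40.6% |
| 50% | 63.7% |

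At 30% this is 0.30 × 15 = 4.5 versus 0.406 × 15 = 6.1 subjects per cohort. It requires every subject in one cohort to leave at Week 26 and every subject in another to stay to Week 38.

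**Step 2: mixed exit.** Suppose 80% of one cohort and 20% of another leave at Week 26, and the rest stay to Week 38.

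- Shorter effect: 0.8 × 30% + 0.2 × 40.6% = 32.1%, or 4.8 of 15.
- Longer effect: 0.2 × 30% + 0.8 × 40.6% = 38.5%, or 5.8 of 15.

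The gap is 6.4 points, about one subject in 15. At 10%, 20% and 50% by Week 26 it is 2.6, 4.7 and 8.2 points.

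**Step 3: events clustered after injection.** Let H = −ln(0.70) = 0.357 be the cumulative hazard to Week 26. Let a share s of it fall early and spread the rest evenly. By Week 38 the incidence is 1 − exp(−[sH + (1 − s)H × 38/26]).

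- s = 0.5: 35.5%
- s = 0.8: 32.3%
- s = 0.9: 31.1%

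The extreme contrast of 10.6 points shrinks to 1 or 2 points when 80 to 90% of the hazard is early.

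**Step 4: scale of chance variation.** The exact 95% interval for 5 of 15 is 11.8% to 61.6%.

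**Step 5: GL-only subjects.** With the constant hazard of Step 1 and 30% by Week 26, 14 weeks gives 1 − 0.70^(14/26) = 17.5%, against 30% at Week 26 and 40.6% at Week 38. This contrast comes from the DRC rule and not from response.

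**Step 6: would a person-time rate be safer?** Take s = 0.9 and divide the percentage with an event by the full weeks of follow-up. The result is 30/26 = 1.15 versus 31.1/38 = 0.82 per 100 subject-weeks. The longer-followed cohort now looks about 29% better (1 − 0.82/1.15), so the distortion has changed sign.

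**The case against.** The strongest reply is that the distortion is small and visible. The drug is given as two injections two weeks apart, so events may cluster early. Injection sites are not evaluated after Week 6 (Protocol 8.4.4), and the DRC reviews each cohort at a common time, Week 5. With 15 subjects per cohort and no formal tests planned (Protocol 9.3), a gap of one subject is well inside the noise. Length of participation and onset days will be reported. All of this stands and limits the size. It does not remove a systematic component whose direction is known in advance, and nothing visible ties the participation summary to the cohort comparison.

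The dose link is also conditional. All four scores must return before exit, two of them are for GL, and GL receives 40 U in every cohort. FHL dose lengthens follow-up only where the forehead is last to return. This stands too.

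A reader might infer three stronger things that the documents do not support:

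- **That the Week 14 end depends on response.** It is a cohort-level DRC decision, and the subjects concerned are outside Safety-FHL. Safety analyses use the treatment actually received (SAP 4), and the text defining the summary groups is partly redacted. How GL-only subjects would be displayed is therefore not known.
- **That the artefact is about 15 points.** That figure takes 40% by Week 24, a constant hazard and everyone leaving at Week 24 in one cohort and Week 38 in another: 40.0% versus 1 − 0.60^(38/24) = 55.5%. The visit schedule does not fit a Week 24 exit, and the rate is invented.
- **That longer-acting cohorts will show more events.** They can; whether they do depends on event timing and on which area returns last.

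Redacted sections and the separate table shells could contain a common-window analysis. None is visible.

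**Conclusion.** The point holds for FHL-treated subjects. The primary safety endpoint is a crude percentage over follow-up that ends between about Week 26 and Week 38 according to the subject's own scores, so a cohort with a longer forehead effect can show a higher percentage at the same true rate. Under an assumed 30% by Week 26, the artificial excess runs from 1 or 2 points (early-clustered events) through about 6 points (mixed exit, constant hazard) to 10.6 points in the extreme case. The mixed-exit figure is about one subject per cohort. These figures rest on the assumed rates and exit patterns, on the follow-up rule working as a true minimum, and on the forehead being last to return often enough for dose to matter.

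Separately, and only if the DRC withholds FHL in a cohort, subjects followed for 14 weeks remain in the Safety population. They should not be set against cohorts with full follow-up without a matching window.

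**What to change.** In SAP 6.6.3, for the Safety-FHL population:

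1. Add a by-cohort TEAE table over a common window, Day 1 through Week 26, with FHL injection through Week 26 shown separately. Name it as the basis for comparing cohorts. Including Day 1 keeps the events between GL and FHL treatment.
2. Use Day 1 to Week 14 for any table that puts GL-only subjects beside other cohorts.
3. Keep the whole-study percentage and show median follow-up by cohort next to it.
4. Treat any exposure-adjusted rate as optional, because it can mislead when events cluster after injection.

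The follow-up passages must also be reconciled in both documents. They give a minimum counted from GL treatment, a different intended minimum counted from FHL treatment (SAP only), and a first-to-occur clause which, read literally, does not let either act as a minimum. Until this is settled, it is not certain that every subject is observed through the common window. The window should end where the reconciled text guarantees observation.

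The cost is SAP wording and one or two tables from dates already collected. The small downside is that the comparison table omits late events, which stay in the whole-study table and the listings.
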